C2. Study design. Participants will be randomly assigned to SBT or ABBT. Treatment will be delivered in 75-minute, small (12-15 participants), closed-group sessions. Groups will be held weekly in months 1-3, biweekly in months 4-6, and monthly in months 7-12, for a total of 25 sessions. Assessments will occur at months 0 (baseline), 1 (midpoint 1), 3 (midpoint 2), 6 (midpoint 3), 12 (post-treatment), and 24 (1-year follow-up).

C3. Alternative designs considered. While we considered a shorter treatment duration (to reduce burden and increase disseminability), we ultimately chose a 25-session treatment for three reasons. First, 25 sessions over 1 year is about the modal length and the recommended intensity for gold standard weight loss treatment. Second, this length is consistent with the increasingly-supported chronic care model of obesity.¹⁵⁷ Third, clinical trial experts have recommended that, for initial tests of efficacy, treatments should be evaluated at full potency to reduce the likelihood that failure occurs because of sub-optimal dosage.¹⁵⁸ If ABBT improves weight loss outcomes for BED, methods for reducing the intensity (e.g. optimization and refinement of session content) and increasing the scalability (e.g. use of alternative delivery methods and/or non-experts clinicians, both of which have been successfully completed with ABBTs for other disorders¹⁵⁹) can be explored in future studies. We also considered including a second follow-up assessment, but determined that given the time needed to recruit and treat 130 participants with BED, a longer follow-up period would not be feasible.

Timeline	Year 1			Year 2			Year 3			Year 4			Year 5			R = recruitment
Manual refinement	X	X														
Therapist training	X															A = assessment (A ₁ , A ₂ , A ₃ , A ₄ , A ₅ = months 0, 3, 6, 12, 24, respectively).
Wave 1	R	A ₁	A ₂	A ₃		A ₄			A ₅							
Wave 2		R	A ₁	A ₂	A ₃		A ₄			A ₅						
Wave 3			R	A ₁	A ₂	A ₃		A ₄			A ₅					
Wave 4				R	A ₁	A ₂	A ₃		A ₄			A ₅				
Wave 5					R	A ₁	A ₂	A ₃		A ₄			A ₅			
Wave 6						R	A ₁	A ₂	A ₃		A ₄			A ₅		
Data analysis														X	X	
Manuscript preparation														X	X	
Planning future studies, e.g. optimization														X	X	

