Primary Aim (Efficacy of ABBT). Analyses will be conducted via linear mixed effects models for longitudinal data, which increase power by fully exploiting the strong correlation in treatment outcomes of interests (i.e., primarily, percent weight loss and secondarily, percent binge frequency reduction) across time. Patterned covariance matrices as implemented in SAS/STAT PROC MIXED V9.2 will be used to evaluate between group differences for percent weight loss and percent binge reduction across the study as a whole, and at each assessment post-baseline.²²⁵ Separate variance components will be used to capture therapist and participant-within-therapist variation. The within-subject covariance matrix will be assumed common across study arms, with an exponential variance function to deal with heteroscedasticity and a continuous-time AR(1) correlation matrix to accommodate residual autocorrelation over the unequal-size time intervals between follow-ups. Outcomes at all six time points will be estimated jointly for maximum statistical efficiency in the presence of intermittent missingness and loss to follow-up. The model will include random effects for subject and time (with higher-order effects if needed to capture nonlinear change), and fixed effects for treatment arm, time by treatment interaction, demographic information, and baseline values of weight, dietary intake and physical activity. Time-specific covariate-adjusted contrasts will be used to compare outcome between groups.

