Primary Aim (Efficacy of ABBT). The study's data will consist of repeated assessments over time within randomized individuals within each treatment condition. Therefore, power calculations are dependent on both an expected difference between treatment arms as well as the clustering of the data (repeated observations within an individual with up to six repeated measures per participant within one of the two treatment conditions), resulting in a multilevel model structure. Using the method described by Raudenbush²⁵²⁻²⁵⁴ and implemented with the software Optimal Design, power calculations were made for this multilevel model structure. No results are available which directly compare the effect of ABBT and SBT on weight loss in BED patients. However, effect size can be predicted by deriving effect sizes from trials with elements similar to the proposed study, e.g., percent weight loss comparison between ABBT and SBT from the Mind Your Health II study (effect size at 12 months $d=0.39$) and percent weight loss and binge reduction comparison of CBT vs. SBT ($d=0.625$; 30% difference in binge reduction rates).⁶⁴ Based on previous studies, we aim to detect a clinically meaningful difference for both weight and binge eating frequency (3.5% weight loss between groups ($d=0.46$) and a difference in 4 binge eating episodes over the 4-week time period). Baseline covariates that can account for variability in the trial outcomes were taken into consideration in the power analysis. Given these assumptions, a sample size of 104 (52 for each group) is required for 80% power with the significant level of 0.05 and five assessment points, assuming the ratio of the variability of level-1 coefficient to the variability of level-1 residual is one. While allowing for up to 20% attrition, the proposed sample size of 130 is adequately powered to examine a clinically meaningful difference between treatment conditions for both percent weight loss and frequency of binge episodes. We believe this power estimate to be conservative given: 1) attrition estimates are greater than the team has achieved in similar weight control studies; and 2) missing values will be imputed using multiple imputation to maximize the number of the observations used to estimate models.

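### Protocol C10 counts month 0 among six outcome time points, although percent change is zero there for everyone; the row adds nothing and weakens covariate adjustment to a degree the documents do not fix

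*Protocol*

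**What the plan says.** Protocol C2 gives the schedule, and C9 repeats it: "Assessments will occur at months 0 (baseline), 1 (midpoint 1), 3 (midpoint 2), 6 (midpoint 3), 12 (post-treatment), and 24 (1-year follow-up"). C10 (Primary Aim) names the modelled outcomes as "primarily, percent weight loss and secondarily, percent binge frequency reduction" and states "Outcomes at all six time points will be estimated jointly for maximum statistical efficiency"; the sentence goes on to tie the efficiency to missed visits and dropout. The random-effects sentence reads "The model will include random effects for subject and time (with higher-order effects if needed to capture nonlinear change"), and the residual model has "an exponential variance function to deal with heteroscedasticity and a continuous-time AR(1) correlation matrix". The fixed effects are arm, time by arm, and "demographic information, and baseline values of weight, dietary intake and physical activity". No covariate-by-time term is listed. Arms are compared "across the study as a whole, and at each assessment post-baseline".

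C11 speaks of "up to six repeated measures per participant" and then bases its sample size on five assessment points. The timeline legend in C3 also lists five assessments, but those include month 0 and omit month 1.

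The SAP analyses percent weight change with a random intercept and quadratic-time slopes. It lists no baseline covariates for the efficacy models and does not say whether month 0 is a response row.

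**The concern.** There are six outcome time points only if month 0 is one of them. Percent change is 100 × (W_t − W_0)/W_0, so at t = 0 it is 0 for everyone in both arms. Limiting the visit-by-visit comparisons to post-baseline assessments restricts the contrasts; it does not remove the month-0 row from the response vector.

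Four consequences follow.

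- The row says nothing about treatment.
- The error model must give positive variance to a quantity that has none.
- A covariate entered as a main effect has one coefficient for all visits, so that coefficient must also fit a visit where its true effect is zero.
- A whole-study average that includes month 0 includes a fixed zero.

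Covariate adjustment matters here because C11 says baseline covariates entered the power calculation.

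**Working it through.** **1. The plan's own figure.** C11 targets 3.5 percentage points at d = 0.46, so SD = 3.5/0.46 = 7.61. At two-sided 0.05 and 80% power, n per arm = 2(1.960 + 0.842)²/0.46² = 74.2, or 75 per arm (150 in all). With a covariate R-squared of 0.30, 74.2 × 0.70 = 51.9, or 52 per arm, which gives the stated 104; 104/0.80 = 130. C11 does not state its R-squared, so 0.30 is an assumption. It is used below because it reproduces 104 in this simple formula. I do not call 104 wrong.

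**2. What adjustment is worth at 52 per arm.** Take SD 7.6 at month 12.
- Unadjusted SE = 7.6 × √(2/52) = 1.490; power = Φ(3.5/1.490 − 1.96) = 65%.
- Fully adjusted SE = 1.490 × √0.70 = 1.247; power = 80%.

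**3. Zero variance at month 0.** An exponential variance function gives σ²·exp(2δ·0) = σ² > 0 at t = 0, and the random intercept adds to it. The true SD there is 0. The fitted SD was 2.1 to 6.4 in the scenarios below.

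**4. Pull on the covariate coefficient.** With a main effect only, the estimate tends to a weighted mean of the visit-specific effects b_t, with weights V⁻¹1/(1′V⁻¹1) from the fitted covariance V. Month 0 contributes b_0 = 0. If the fitted coefficient is k times the true month-12 effect, the share of the month-12 variance reduction retained is 1 − (1 − k)².

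I took the large-sample limit of the C10 model (random intercept and slope, exponential variance, continuous-time AR(1), a separate arm effect at each visit) with and without month 0. Assumptions, none of them in the documents:
- R-squared 0.30 at month 12;
- total SD either 7.6 throughout or rising as 2, 4, 6, 7.6, 8.5 over months 1 to 24;
- correlation between months s < t of ((s+1)/(t+1))^0.35;
- complete data.

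In scenario B a constant effect of √0.30 × 7.6 = 4.16 exceeds the assumed total SD at months 1 and 3, so residual variance there was floored at 15% of the squared SD.

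| Scenario | Rows | k | Retained | True SE | Model SE | Power | Actual size of 5% test |
|---|---|---|---|---|---|---|---|
| A: SD rises, covariate effect grows with it | 6 | 0.17 | 30% | 1.42 | 1.24 | 69% | about 9% |
| | 5 | 0.34 | 57% | 1.36 | 1.13 | 73% | about 10% |
| B: SD rises, effect constant | 6 | 0.62 | 86% | 1.29 | 1.10 | 78% | about 9% |
| | 5 | 1.00 | 100% | 1.25 | 1.21 | 80% | about 6% |
| C: SD and effect constant | 6 | 0.82 | 97% | 1.26 | 1.10 | 80% | about 9% |
| | 5 | 1.00 | 100% | 1.25 | 1.17 | 80% | about 7% |

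SEs and power refer to month 12. Actual size is 2[1 − Φ(1.96 × model SE/true SE)].

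Over 18 settings, which also varied the form of the error model, the retained share with month 0 ran from 14% to 98% and was below 50% in 4.

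**5. Whole-study contrast.** If arm differences δ_1 to δ_5 are averaged with a fixed zero, the result is (Σδ)/6 = (5/6) × (Σδ)/5. A constant 3.5-point difference would be reported as 2.9.

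**The case against.** The size depends on assumptions, and in most settings it is modest. A reader might infer that month 0 cancels most of the covariate adjustment. The documents do not support that as a general statement: they give no covariate R-squared, no SD by visit and no indication whether the covariate effect grows. Most of the adjustment is lost only when that effect grows with time. Even then the row is only part of the cause. In scenario A deleting it lifts retention from 30% to 57%, and the remaining loss comes from the missing covariate-by-visit term.

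Deleting month 0 does not reliably repair the standard errors either. Calibration improves in scenarios B and C and worsens slightly in A. In a random-quadratic variant the model SE with month 0 was too large rather than too small, by up to about 22%.

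A reader might also infer that month 0 inflates the false-positive rate in the SAP's models. The SAP does not say that month 0 is a response row, and its random-effects wording can be read in more than one way. With rising SDs and a random intercept plus quadratic-time slope, but no random linear slope, the joint arm-by-time test ran at 16–23% with month 0 and 9–17% without. With correlated random intercept, linear and quadratic terms it ran at 4.6–4.9% and 4.3–5.0%. No inflation figure can therefore be attached to the SAP as written. The covariate point does not reach it either, because its efficacy models list no baseline covariates.

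Finally, six is a correct count of visits in C11, and no power figure is shown to rest on it. These limits all stand. None of them removes the month-0 row from C10.

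**Conclusion.** The point holds for the protocol's primary model. C10 makes month 0 a response row for outcomes that are zero there by construction, and no text removes it. The row adds no treatment information, does not fit the error model, and pulls main-effect covariate coefficients toward zero: 0.17 to 0.82 of the month-12 value with it, 0.34 to 1.00 without it. The loss of adjustment ranges from slight to most of it. In the three scenarios month-12 power falls by 0 to 4 points, given an R-squared of 0.30 and the assumed SDs and correlation.

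With complete data and a separate arm effect at each visit, the treatment contrast is unbiased; the harm is to precision and SE calibration. This check does not cover the SAP's polynomial time trend. The 5/6 dilution applies only if the whole-study contrast averages all six points, which C10 leaves open. The change is worth making because it is specific and cheap; the documents do not show that the trial's conclusion depends on it.

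**What to change.** - For percent-change outcomes, use months 1, 3, 6, 12 and 24 as the response rows, and let each baseline covariate's effect differ by visit. Dropping month 0 without the covariate-by-visit terms is only a partial cure.
- For weight, an alternative is to model log weight at all six visits with the arms constrained equal at month 0, then back-transform to percent change.
- Define the whole-study contrast as an average over the five post-baseline visits.
- In C10, change six to five for the percent outcomes.
- In the SAP, state that month 0 is not a response row.

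The cost is a few lines of text, a few extra covariate-by-visit parameters and a small amount of re-analysis, the last only where month 0 was in fact included.

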and overeating episodes without loss of control in BED is elevated negative affect and distress intolerance (i.e., the perceived inability to tolerate negative emotional states).³⁸⁻⁴² For example, one recent study found that among patients with BED, days characterized by high or increasing negative affect were associated with a greater likelihood of either a binge episode or an overeating episode without loss of control occurring on that day.⁴³ Although binge eating often begins as an impulsive attempt to regulate negative emotion^{39, 44-48}, persistent binge eating can lead to a compulsive use of eating as a way to regulate emotions^{45, 49} and reduce access to more adaptive coping strategies.^{45, 50} Ultimately, eating becomes one of very few “tools in the tool-kit” for reducing distress.⁵⁰ As seen in the figure above, elevated food reward sensitivity, overvaluation of shape and weight, and negative affect and distress intolerance directly and indirectly (e.g., by increasing rigid dietary restraint) contribute to binge eating, overeating episodes without loss of control, and an elevated BMI in patients with BED. These widely accepted maintenance factors for BED reflect areas where treatments can intervene to reduce overeating episodes with and without loss of control. However, existing behavioral treatments for BED fail to adequately address these shared maintenance factors.

A4. Cognitive behavioral therapy effectively reduces binge eating, but fails to improve weight.

The current gold-standard treatment for reducing binge eating in BED is Cognitive Behavioral Therapy (CBT)⁵¹, which uses cognitive and behavioral techniques to regularize eating, reduce dietary restraint, and alter the cognitive manifestations of BED.²⁹ CBT for BED is superior to other treatments in eliminating binge eating, with up to 60% of patients achieving full remission from binge eating.⁵¹ However, despite success in reducing binge eating, CBT fails to produce clinically significant weight loss in BED.⁵¹⁻⁵³

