As described above, incorporating physical activity into treatment for BED both reduces binge episodes^{87, 88} and encourages weight loss.^{54, 55, 87-89} For example, one study found that for patients with BED, CBT plus nutritional counseling alone was less effective at producing weight loss than CBT plus nutritional counseling and physical activity.⁸⁸ Only participants in the physical activity condition experienced reductions in drive for thinness, suggesting that physical activity may also target overvaluation of weight and shape. Physical activity is known to reduce depressive symptoms in patients with BED, and reduces the impact of anxiety sensitivity (e.g., fear of anxiety and related sensations, conceptually related to distress intolerance) on binge eating pathology, perhaps because physical activity functions as a coping strategy and reduces reliance on binge eating as a way to reduce emotional distress.¹¹⁶ A recent systematic review of physical activity for BED concludes that adding exercise to behavioral treatments for BED can facilitate reduced binge eating and weight loss both directly (e.g., by burning calories) and indirectly (e.g., by improving depression, reducing reliance on binge eating to reduce emotional distress).¹¹⁷ Despite the many known benefits of physical activity, existing treatments either do not include any physical activity (CBT) or target physical activity as only a secondary goal of treatment given evidence that reducing caloric intake is more important for producing initial weight loss (BWL).^{72, 118} Greater session time devoted to physical activity and a focus on physical activity as a primary method for directly and indirectly reducing binge eating and facilitating weight loss appears warranted.

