
Values clarity/commitment enhancement. Consistent with principles of ACT¹²⁰ and intrinsic motivation theory¹⁷⁹, ABBT will emphasize that participants must choose goals that emanate from freely-chosen, personal life values (e.g., living a long and healthy life; being a present, active mother). A structured process for the identification of such life values will be followed and the connections between these values and eating and physical activity behaviors will be emphasized. Participants will be taught that commitment to difficult behavioral goals is only likely to be maintained when one connects psychologically with life values important enough and meaningful enough to make such effort and sacrifice worthwhile. Commitment will be presented as a critical component of maintaining changes to the personal food and physical activity environment. Values clarity interventions will also be used to alter overvaluation of weight and shape. An underlying assumption about values is that they are finite; that is, there is a limit to what can be encapsulated in an individual's value base. Thus, the overvaluation of weight and shape that occurs in BED necessitates that there is less "room" for other valued domains.¹²⁸ By helping patients pursue committed actions towards personal values, ABBT may be able to foster awareness of the values-inconsistent nature of binge eating and overeating episodes, reduce overvaluation of weight and shape, and improve motivation for adherence to program goals.

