Secondary Aim 1 (Between-Subjects Mediation). We will examine the extent to which variables of interest (i.e., dietary restraint, adherence to caloric and physical activity goals, negative affect and distress tolerance, overvaluation of shape/weight, and values clarity) will mediate differences in weight loss and reduction in binge eating between treatments. Specifically, we will determine whether temporally-precedent changes in each mediator from baseline to 1 month and baseline to 3 months mediate subsequent differences in weight loss at 6, 12 and 24 months respectively. We will use the mediation model outlined by Preacher and Hayes and Mplus version 6.12 to estimate the total and specific indirect effects of each hypothesized mediator individually.^{230, 231} This approach expands on Baron and Kenny's methods by providing additional guidelines and techniques that allow for the most robust and accurate interpretation of these mediating effects.^{232, 233} Confidence intervals for the indirect effects will be generated using the bias-corrected (BC) bootstrapping approach.²³⁴

Secondary Aim 2 (Between-Subjects Moderation). Reward sensitivity, overvaluation of shape/weight, negative affect, and distress tolerance will be added to the model described in Aim 1, and allowed to interact with time and treatment arm, to determine whether these variables moderate the effect of treatment.

Statistically significant interactions will be interpreted by plotting simple regression lines for each variable.²³⁵

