Secondary Aim 1 (Between-Subjects Mediation). Tests of mediation will utilize bias-corrected bootstrapping which demonstrates the best balance of statistical power and type I error.²⁵⁵⁻²⁵⁷ Fritz and MacKinnon²⁵⁵ documented sample size requirements to guarantee 80% power at a significance level of 0.05 for regression-based mediation models. Under the assumption of small to medium effect sizes for intervention with the mediator and for the mediator on outcome controlled for intervention, a sample size of 130 (58 per group) is required to achieve 80% power.^{241, 244, 255} Given a sample size of 130 and the pattern of weight loss and attrition described above, we will be sufficiently powered to evaluate our hypothesized effects.

Secondary Aim 2 (Between-Subjects Moderation). In the linear mixed models used for the primary hypotheses, we will add as covariates both the main effects of our proposed moderators and their interactions with intervention assignment. Given $N=130$ and the pattern of weight loss, binge reduction, and attrition described above, we will have 80% power to detect moderation if the standardized coefficient for the treatment x moderator interaction is ≥ 0.3 (accounts for at least 8% of the variance) in a model in which the total variance accounted for is $\geq 20\%$.

REFERENCES

1. Bellows, B.K., S.L. DuVall, A.W. Kamauu, D. Supina, T. Babcock, and J. LaFleur, *Healthcare costs and resource utilization of patients with binge-eating disorder and eating disorder not otherwise specified in the Department of Veterans Affairs*. International Journal of Eating Disorders, 2015
2. Association, A.P., *Diagnostic and Statistical Manual of Mental Disorders (DSM-5®)*. 2013: American Psychiatric Pub.
3. Hudson, J.I., E. Hiripi, H.G. Pope, and R.C. Kessler, *The prevalence and correlates of eating disorders in the National Comorbidity Survey Replication*. Biological Psychiatry, 2007. **61**(3): p. 348-358
4. Mitchell, J.E., *Medical comorbidity and medical complications associated with binge-eating disorder*. International Journal of Eating Disorders, 2015
5. Fandiño, J., R.O. Moreira, C. Preissler, C.W. Gaya, M. Papelbaum, W.F. Coutinho, and J.C. Appolinario, *Impact of binge eating disorder in the psychopathological profile of obese women*. Comprehensive Psychiatry, 2010. **51**(2): p. 110-114
6. Mitchell, J.E. and M.P. Mussell, *Comorbidity and binge eating disorder*. Addictive Behaviors, 1995. **20**(6): p. 725-732

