For Secondary Aim 1, mediation analyses were conducted using the R “lavaan” structural equation modeling package (Rosseel, 2012). Mediation analyses estimated the indirect effect of treatment condition through change in each mediator from baseline to 3-months on percent change in weight, binge eating frequency change, and global eating disorder psychopathology change at post-treatment and through changes from baseline to 6-months on weight, binge eating frequency change, and global eating disorder psychopathology change at one year follow-up. Baseline levels of the dependent variable and mediator were included as covariates in mediation models. Physical activity minutes and VLQ scores were z-score normalized to correct for significantly larger variances.

References

Knowles, J. E., Frederick, C., Whitworth, A., & Knowles, M. J. E. (2023). Package 'merTools'.

Rosseel, Y. (2012). lavaan: An R package for structural equation modeling. *Journal of statistical software*, 48, 1-36.

Selya, A. S., Rose, J. S., Dierker, L. C., Hedeker, D., & Mermelstein, R. J. (2012). A practical guide to calculating Cohen's f^2 , a measure of local effect size, from PROC MIXED. *Frontiers in Psychology*, 3, 111.

Van Buuren, S., & Groothuis-Oudshoorn, K. (2011). mice: Multivariate imputation by chained equations in R. *Journal of statistical software*, 45, 1-67.

Wing, R. R., Tate, D. F., Gorin, A. A., Raynor, H. A., & Fava, J. L. (2006). A self-regulation program for maintenance of weight loss. *New England Journal of Medicine*, 355(15), 1563-1571.

Zhang, Y. W. (2013). CPLM: compound Poisson linear models. *A vignette for R package cplm*. Available at <http://cran.r-project.org/web/packages/cplm>, 619, 621.

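### The mediation models test each mediator separately and adjust only for two baselines, so they cannot show which mechanism drives the effect

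*Protocol*

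**What the plan says.** Protocol C10, Secondary Aim 1, names the candidate mediators as "dietary restraint, adherence to caloric and physical activity goals, negative affect and distress tolerance, overvaluation of shape/weight, and values clarity", which is at least six constructs. The method is "to estimate the total and specific indirect effects of each hypothesized mediator individually", with bias-corrected bootstrap intervals.

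The SAP's paragraph on Secondary Aim 1 matches separate models. The analyses "estimated the indirect effect of treatment condition through change in each mediator from baseline to 3-months" for the post-treatment outcomes, and used change to 6 months for the one-year follow-up. On adjustment it says: "Baseline levels of the dependent variable and mediator were included as covariates in mediation models". It lists no other covariate.

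Neither document describes a model holding several mediators, or a sensitivity analysis for mediator-outcome confounding. By contrast, the primary efficacy model in protocol C10 adjusts for demographics and for baseline weight, dietary intake and physical activity. Protocol C5 stratifies randomisation by BMI category, sex, race/ethnicity and binge frequency. Protocol C9 collects the BDI-II at every assessment.

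**The concern.** An indirect effect is the product of two paths. Randomisation makes the first (arm to mediator) causal. The second (mediator to outcome, given arm) compares participants whose mediators changed by different amounts for reasons nobody randomised. Two things can then produce an apparent indirect effect:

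- **A shared baseline cause.** A factor that predicts both mediator change and outcome biases the second path.
- **Cross-crediting.** If two mediators both respond to treatment and are correlated within arms, a model holding only one of them gives it part of the other's effect.

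The protocol's own theory makes such links likely. Section A3 says that food reward sensitivity, overvaluation, and negative affect with distress intolerance "directly and indirectly (e.g., by increasing rigid dietary restraint) contribute to binge eating". Section A7 says "Physical activity is known to reduce depressive symptoms in patients with BED". Section C6b says "Values clarity interventions will also be used to alter overvaluation of weight and shape".

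The aim is to learn which mechanism explains a difference between arms. With separate, lightly adjusted models, several mechanisms could each look confirmed when only one is active.

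**Working it through.** **1. The plan's own figure.** Protocol C11 cites "sample size requirements to guarantee 80% power at a significance level of 0.05 for regression-based mediation models" and states 130 participants (58 per group), for paths described only as small to medium. Since 2 × 58 = 116, the total and the group size disagree. Assuming both standardised paths are 0.26, simulated bias-corrected bootstrap power for one mediator is 78.9% at N=130, 72.2% at 116 and 66.5% at 104 (130 × 0.8, after 20% attrition). So 130 is reproducible under that assumption, for one mediator at a time. The point below does not depend on it.

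**2. Size of the cross-credit.** Let treatment move mediators 1 and 2 by a, let only mediator 2 affect the outcome (b₂), and let their within-arm correlation be ρ. In large samples the single-mediator model gives inert mediator 1 a spurious indirect effect of a × b₂ × ρ. With a = 0.26 and b₂ = 0.39:
- ρ = 0: 0
- ρ = 0.3: 0.26 × 0.39 × 0.3 = 0.030
- ρ = 0.5: 0.051
- ρ = 0.7: 0.071

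**3. How often an inert mediator is declared significant.** The values of ρ and of the paths are assumptions.

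Joint-significance test, n=104, arm shift 0.5-0.8 SD, causal path 0.4:

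| ρ | Single model | Joint model |
|---|---|---|
| 0.3 | 15-19% | 3-6% |
| 0.5 | 36-47% | 3-6% |

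At ρ = 0 the single model is at about the nominal rate. Repeat runs agree to within about three points.

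Bias-corrected bootstrap (the protocol's method), a = 0.26, b₂ = 0.39:

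| ρ | Single, n=104 | Single, n=130 | Joint (both n) |
|---|---|---|---|
| 0 | 7% | 7% | 6-7% |
| 0.3 | 25% | 31% | 9-10% |
| 0.5 | 49% | 61% | 7-8% |
| 0.7 | 70% | 80% | 7-9% |

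**4. Omitted baseline cause, no true mediation.** With n=104 and a cause correlated 0.3-0.4 with mediator and outcome:
- no baseline adjustment: 10-37% false mediation
- the two planned baselines adjusted: 7-24%
- the cause itself also adjusted: 4-5%

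The planned baselines help, but incompletely.

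**5. What a joint model does not cure.** If an outside cause loads 0.5 on both mediators and on the outcome, the false indirect effect is 0.26 × 0.258 = 0.067 in the single model and 0.26 × 0.206 = 0.054 in the parallel model. It reaches about zero only when the cause is adjusted.

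**6. What a parallel model can get wrong.** In a chain arm → M1 → M2 → outcome, with arm effect 0.5-0.8 SD, M1-M2 slope 0.5 and M2-outcome slope 0.4, the true indirect effect through M1 is 0.5 × 0.5 × 0.4 = 0.10 to 0.8 × 0.5 × 0.4 = 0.16. The single-mediator model recovers it and detects it in 33-48% of trials. The parallel model estimates about 0 and detects it in about 5%.

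**7. Power in a joint model.** Holding a second mediator inflates the variance of the second path by 1/(1 − ρ²), which is 1.33 at ρ = 0.5 and 1.96 at 0.7. With N=130 and a = b = 0.26, joint-significance power falls from 72% at ρ = 0 to 62% at 0.5 and 48% at 0.7. With six mediators, n=104 and path 0.4, power falls from 70% to 61% (arm shift 0.5 SD) or 95% to 81% (0.8 SD) at ρ = 0.5. At 0.7 it falls from 70% to 46% or 96% to 63%.

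**The case against.** The strongest case for the plan has five parts.

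- **A single-mediator indirect effect is a coherent quantity.** This stands. The word 'specific' is in the protocol only; the SAP speaks simply of the indirect effect. A reader might infer that the SAP claims mutually adjusted effects. It does not, and the labelling problem lies in the protocol's wording, where 'specific' sits badly with 'individually'.
- **A parallel model could erase the mechanism the theory proposes.** This also stands. Sections A3 and C6b describe chains, and step 6 shows a genuine upstream effect vanishing when the downstream mediator is held fixed. A reader might infer that one parallel model should replace the separate ones. The documents do not support that, and step 7 shows it would be costly.
- **The percentages are not properties of this trial.** Correct. No correlation between mediators is given, and at zero there is no cross-crediting.
- **Some proposed covariates overlap with those planned.** True in part. Baseline binge frequency is already in the binge models, baseline weight overlaps BMI category, and the BDI-II may itself be a mediator baseline. Sex, race/ethnicity and age are not covered. The protocol's primary model already adjusts for demographics, so including them here is consistent.
- **The aim is secondary, mediator change precedes the outcome visit, and the SAP is written in the past tense.** All true. Temporal order rules out some reverse causation but not shared causes, and added analyses would have to be labelled post hoc.

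**Conclusion.** The concern holds in limited form. The separate models leave the mediator-to-outcome path exposed to measured baseline confounders and to cross-crediting, and neither document provides a check on either. In the joint-significance runs with 104 completers, cross-crediting raises false mediation from about nominal at correlation 0 to 15-19% at 0.3 and 36-47% at 0.5; the bootstrap runs gave higher rates. An omitted baseline cause of moderate strength gives 7-24% after the planned adjustment, against 4-5% once included. These figures rest on assumed paths and correlations, and on reading the SAP's covariate list as complete.

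A reader might go further and infer that the mediation findings are false, or that the separate models are invalid. The documents do not support either: they give no correlations, and under a causal chain the separate model is the one that recovers the upstream effect. What the separate models cannot support is a claim that one mechanism rather than another drives the result. Because the extra covariates are stratification factors or are already collected, that part of the remedy is worth making for a secondary aim.

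**What to change.** 1. In both equations of every mediation model, add the randomisation strata (BMI category, sex, race/ethnicity, binge frequency), age and baseline BDI-II, where not already included.
2. Keep the separate models, but report their results as single-mediator indirect effects that are not mutually adjusted, and drop 'specific'.
3. Add a multiple-mediator model as a supporting analysis, with one measure per construct. Make it serial where the protocol posits a chain, such as values clarity to overvaluation, or overvaluation and affect to rigid restraint.
4. Do not conclude from the separate models alone that one mechanism rather than another drives the effect.
5. Since the SAP describes completed analyses, label the additions post hoc and show them beside the existing results.

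**Cost:** a few degrees of freedom for the covariates, and one supporting model per outcome and visit (3 outcomes × 2 visits = 6). The supporting model will lose material power if the six or so constructs are highly correlated (step 7), so a non-significant path in it should not be read as absence of mediation. Baseline covariates do not remove shared causes that arise after baseline, and the report should say so.
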